	 with the written approval of the Sponsor or Medical Monitor 9. Abnormal clinically significant laboratory test values at screening that, in the opinion of the Sponsor or Medical Monitor would preclude study participation 10. Known history of allergy/hypersensitivity to amphetamine or any of the components of DYANAVEL XR, heparin flush and topical anesthetics 11. Parent or guardian's inability or unwillingness to follow directions of the Investigator or study research staff 12. Any uncontrolled medical condition that in the opinion of the Sponsor or Medical Monitor would preclude study participation 13. History of significant illness requiring hospitalization, or surgery requiring anesthetics within 30 days of dosing.
Assessments:	 K-SADS-PL Adverse Events Electrocardiogram Safety Labs Physical Exam Vital Signs Medical History Concomitant Medications
Criteria for evaluation:	Pharmacokinetics : The pharmacokinetic parameters for the concentrations of d- and l-amphetamine in plasma will be determined for each subject receiving study medication.
Statistical methods:	 Sample size determination: The sample size for this study was powered per FDA instruction. 4 - 6 subjects aged 4 to 5 years will provide adequate power for a pharmacokinetic analysis. Study populations: Adverse events will be reported for all subjects once enrolled. Total and treatment-emergent adverse events will be reported. All subjects with sufficient plasma concentration data for estimating pharmacokinetic parameters will be included in the pharmacokinetic analyses. Pharmacokinetic analysis: Pharmacokinetic parameters will be summarized and no formal comparisons will be made. Pharmacokinetic plasma samples: All PK Plasma samples will be sent frozen to the analytical lab after the end of the study. Safety analysis: MedDRA, current version will be used to classify all AEs with respect to system organ class and preferred term.
Safety:	Adverse Event (AE) collection

TABLE OF CONTENTS

SPONSOR'S	SIGNATURE	2
INVESTIGAT	OR'S SIGNATURE	3
PROCEDURE	S IN CASE OF EMERGENCY	4
TABLE OF CO	ONTENTS	8
LIST OF ABB	REVIATIONS	. 11
1.0	INTRODUCTION	. 13
2.0	STUDY OBJECTIVE	. 15
3.0	INVESTIGATIONAL PLAN	. 16
3.1	Overall Study Design	. 16
3.2	Rationale for Study Design and Control Groups	. 16
4.0	SELECTION AND WITHDRAWAL OF SUBJECTS	. 18
4.1	Inclusion Criteria	. 18
4.2	Exclusion Criteria	. 18
4.3	Discontinuation of Subjects	. 19

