1.0 INTRODUCTION

Amphetamine has been a well-established therapeutic agent for the treatment of Attention Hyperactivity Disorder (ADHD) for decades. Since the original amphetamine approval, various dosage forms have been approved for use:

- Immediate release (IR) dosage forms, oral solution and tablets.
- extended release (ER) dosage forms, capsules, and tablets with various release technologies

DYANAVEL XR is an extended-release oral suspension that contains 2.5 mg/mL amphetamine base. Drug-resin complexation is formed with the amphetamine and Sodium Polystyrene Sulfonate USP, an ion exchange resin. The extended release feature of the product is achieved by coating some drug/resin complexes with an extended-release coating. DYANAVEL XR contains approximately a 3.2:1 ratio of d-amphetamine compared to l-amphetamine.

The efficacy of DYANAVEL XR in the treatment of ADHD in children ages 6-12 has been established in a Phase 3 placebo-controlled laboratory classroom study: TRI102-ADD-001. ADHD symptoms in children on an individually optimized dose of amphetamine (range 10-20 mg/day) were significantly lower compared to symptoms experienced by children treated with placebo. Symptom control was demonstrated 1 hour after dosing and efficacy was observed through 13 hours beyond dosing. The effect size in this study was in line with effect sizes demonstrated for other psychostimulants tested in a similar study design. The adverse events in this study were expected for amphetamine treatment with respect for type frequency and severity of adverse event.

Study TRI102-PPK-200 was conducted in children ages 6 to 12 years old with ADHD to evaluate the single-dose (10 mg) pharmacokinetics of orally administered DYANAVEL XR. Following a single 10 mg oral dose of DYANAVEL XR in 12 pediatric subjects under fasting conditions, d-amphetamine and l-amphetamine peak plasma concentrations occurred at a median time of 3.9 and 4.5 hours after dosing, respectively. The mean plasma terminal elimination half-life of d-amphetamine was 10.43 (\pm 2.01 h) hours and the mean plasma terminal half-life for l-amphetamine was 12.14 (\pm 3.15 h) hours.

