Study 2014-3401 was conducted in 29 healthy adult subjects in a crossover study under fasting conditions, following a single, 18.8 mg oral dose of DYANAVEL XR, d-amphetamine and l-amphetamine, the median (range) time to peak plasma concentrations (T_{max}) were 4.0 (2 – 7) hours after dosing and peak concentration (C_{max}) were 102% and 106%, respectively of the C_{max} of immediate-release (IR) mixed amphetamine salts tablets. The relative bioavailability of DYANAVEL XR compared to an equal dose of mixed amphetamine salts IR tablets is 106% of d-amphetamine and 111% for l-amphetamine.

See the DYANAVEL XR Package Insert for further information¹.

The present study will fulfill a part of the Phase 4 Commitments Tris Pharma has made to conduct the following FDA required post-marketing studies in children aged 4-5 years with ADHD:

- 2970-1 A single-dose, open-label pharmacokinetic study of DYANAVEL XR (amphetamine) extended-release oral suspension, in children aged 4 to 5 years with ADHD
- 2970-2 A randomized, double-blind, placebo-controlled, flexible-dose titration study of DYANAVEL XR (amphetamine) extended-release oral suspension in children aged 4 to 5 years diagnosed with ADHD.
- 2970-3 A one year Pediatric Open-Label Safety Study of patients aged 4 to 5 years diagnosed with ADHD treated with DYANAVEL XR (amphetamine) Extended-Release oral suspension.

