2.0 STUDY OBJECTIVE

The objective of this study is to evaluate the plasma amphetamine concentration/time profile of DYANAVEL XR in children aged 4 to 5 years with ADHD following a single 2.5 mg dose of DYANAVEL XR.

These data will guide appropriate dosing in planned safety and efficacy studies with DYANAVEL XR in a preschool population with ADHD.

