3.0 INVESTIGATIONAL PLAN

3.1 Overall Study Design

This is an open-label, single-dose study in 4 -6 pediatric subjects with ADHD and who are otherwise healthy. Subjects will receive a single 1 mL dose of DYANAVEL XR (amphetamine) Extended-Release oral suspension 2.5 mg/mL.

Pharmacokinetics will be assessed over a 28 hour period after the single dose. Subjects may be kept at the study site(s) overnight.

Subjects with ADHD aged of 4 to 5 years will be enrolled at up to 2 study sites. Subjects will be screened for participation in the study within 6 weeks before study drug administration. Medical history, physical examination including height and weight, baseline laboratory testing, 12-lead electrocardiogram (ECG), vital sign measurements, a structured diagnostic interview (K-SADS-PL), and informed consent will be completed during the screening visit.

All subjects currently taking an ADHD medication including all psychostimulants methylphenidate, d-methylphenidate, amphetamines or derivatives of any of these products; must not take these medications for 48 hours prior to dosing with study medication. The ADHD medication can be resumed after the 28 hour sample is taken on Day 2, the final day of the study. The investigator should direct all other approved daily medications (see concomitant medications).

Subjects will be confined at the study center prior to dosing until approximately 13 hours postdose, or may stay until the 28 hour blood sample per principal investigator discretion.

Serial blood samples will be collected from all subjects at predetermined time points. The pharmacokinetic parameters of interest will include peak (maximum) observed plasma drug concentration (C_{max}), time to C_{max} (t_{max}), area under the concentration-time curve (AUC) from Time 0 to last sampling time (t) with a quantifiable plasma drug concentration (AUC_{0-t}), AUC from Time 0 to infinity (AUC_{0-∞}), and terminal-phase elimination half-life ($t_{\frac{1}{2}}$).

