3.2 Rationale for Study Design and Control Groups

This study will evaluate the pharmacokinetic properties of DYANAVEL XR, administered orally to pediatric subjects aged 4 to 5 years with ADHD. Objective pharmacokinetic measurements will occur over 28 hours post-dose as a primary endpoint; therefore, an open-label, single-dose study design will be used. Due to the pharmacokinetic focus of this study, no placebo control group will be used.

One age group of pediatric subjects will be included in this study. The children will be aged 4 to 5 years on the day of enrollment into this study. Subjects will receive a 1 mL (2.5 mg) dose of DYANAVEL XR.

Dose Rationale: The dose range of the final optimal dose in a recent pivotal Phase 3 study of DYANAVEL XR in the treatment of children aged 6-12 years with ADHD (n=108) (TRI102-ADD-001) was 10 mg/day to 20 mg/day. None of the 108 subjects enrolled in that study discontinued due to an AE. There were no SAEs, deaths or severe AEs reported. Dosing was initiated at 1 to 2 mL (2.5 to 5 mg)/day (investigator's choice) and was titrated in 1 - 4 mL (2.5

to 10 mg) increments every 4 to 7 days until an optimal dose or the maximum dose (20 mg/day) was reached. Subjects had to reach a final optimal dose between 10 to 20 mg/day, inclusive. No subjects discontinued the study due to inability to tolerate a 10 mg dose.

The mean final optimized dose was 15.4 or 0.47 mg/ Kg. According to the CDC Growth $Chart^2$, the expected weight range with 3rd and 97th percentiles for a pediatric population ages 4 - 6 years is 12 - 24 Kg. Considering the low and high end of the weights for children aged 4 to 5 years, a single dose of 2.5 mg translates to a weight-based dose ranging between 0.21 mg/Kg and 0.11 mg/Kg, less than half of the mean weight-based dose that was well-tolerated in the previous study in children aged 6 to 12 years. Therefore it can be concluded that a single 2.5 mg dose of DYANAVEL XR is expected to be safe and tolerable to pediatric subjects aged 4 to 5 years with ADHD.

Meals: The study will be conducted with meals, snacks and beverages provided ad lib. Rationale: In adult volunteers, DYANAVEL XR had no food effect. Blood draws can be difficult in children, especially when not well-hydrated. Food intake may help reduce emesis (common in children during fasting PK studies) and may reduce vasovagal responses during blood draws.

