Timing of PK sample collection: The main goal is to limit samples on the day of dosing to no more than 8 samples (pre-dose plus 7 post-dose samples) in order to collect an adequate amount of data while keeping the study feasible to conduct. The following collection times have been selected to meet goals of adequate data collection and study feasibility: Pre-dose and 1, 3, 4, 6, 8, 10, 12, and 28 hours post-dose.

With the exception of the 0 (pre-dose) and the 28 hour sample, samples will be collected within ± 15 minutes of the scheduled post-dose time. The pre-dose sample may be collected up to 2 hours before dosing. The 28 hour sample may be collected within 2 hours of the scheduled time. Actual times will be recorded for all events, and any deviation outside the specified ranges must be clearly documented in the subject's case report forms.

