10.2 Study Endpoints

10.2.1 Pharmacokinetic Endpoints

The pharmacokinetic parameters for the concentrations of d- and l-amphetamine in plasma will include C_{max} , t_{max} , AUC_{0-t} , $AUC_{0-\infty}$, and $t_{\frac{1}{2}}$. Mean, geometric mean, standard deviation, and percentage coefficient of variation will be calculated for the pharmacokinetic data, within the context of limited samples which can be collected from a pediatric population.

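### Does section 10.2.1 need a median, minimum and maximum for tmax?

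*Combined protocol and SAP*

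**What the plan says.** Section 10.2.1 lists Cmax, tmax, AUC0-t, AUC0-∞ and t½ for d- and l-amphetamine and then gives one set of summaries for all of them: "Mean, geometric mean, standard deviation, and percentage coefficient of variation will be calculated for the pharmacokinetic data". It makes no exception for tmax.

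No other section adds a median or a range. Section 3.1 names the parameters ("The pharmacokinetic parameters of interest will include peak (maximum) observed plasma drug concentration" and so on) without statistics. The synopsis, under Statistical methods, says only "Pharmacokinetic parameters will be summarized and no formal comparisons will be made". Section 10.5.7 commits to estimating every parameter for each treated subject and names no summary statistic.

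The Introduction (section 1.0) describes earlier data differently. In children aged 6 to 12, "peak plasma concentrations occurred at a median time of 3.9 and 4.5 hours after dosing" for d- and l-amphetamine respectively. In adults it gives "the median (range) time to peak plasma concentrations" as 4.0 h (2 to 7 h).

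On sampling times, section 3.2 says "Actual times will be recorded for all events". Section 5.1.3.1 repeats this, and Appendix B requires the date and clock time of each sample.

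**The concern.** Observed tmax is tied to the sampling schedule and often skewed, so it is natural to report its median with minimum and maximum, as the Introduction does for the earlier studies. As written, the planned tmax summary would not match the form of the only earlier tmax values in the document, and it would give no range.

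This study is purely descriptive, so its summaries are its result. Section 2.0 gives them a use: "These data will guide appropriate dosing in planned safety and efficacy studies". If a mean were read against an earlier median, or if one late peak among 4 to 6 children were hidden inside an SD, a reader could misjudge how the time to peak in preschool children compares with that in older children. One sentence would add the missing statistics.

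**Working it through.** The plan states no sample size, power or error rate that depends on this point, so there is no planned figure to reproduce. Three checks apply.

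**1. How far apart can the listed and unlisted statistics be?**

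Inputs from the protocol: 4 to 6 subjects (section 10.1); post-dose samples at 1, 3, 4, 6, 8, 10, 12 and 28 h, within ±15 minutes except ±2 h at 28 h (section 3.2); earlier medians in children of 3.9 and 4.5 h (section 1.0).

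Assumptions: tmax is lognormal with CV 20, 30 or 40%. The documents give no CV for tmax.

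Method: draw n = 4 or 6 values as median × exp(σZ), with σ² = ln(1 + CV²). Move each to the nearest sampling time and add a uniform deviation within the window. This gives 12 settings of 200,000 trials each.

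| Quantity | Across the 12 settings |
|---|---|
| Geometric mean minus median, average | -0.06 to +0.09 h |
| Same gap at least 0.5 h in size | about 2 to 28% of trials |
| Same gap at least 1 h in size | 0 to 4.5% of trials |
| Arithmetic mean minus median, average | 0.07 to 0.30 h |
| Minimum-to-maximum width, average | 1.6 to 4.7 h |

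The upper ends of the gap frequencies and of the range width come from CV 40%. The sampling interval near the expected peak is 1 h (3 to 4 h) or 2 h (4 to 6 h), so the average difference between geometric mean and median is less than a tenth of the narrower interval.

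The median is not the steadier summary either. Its trial-to-trial SD is larger than the mean's in 10 of the 12 settings, for example 0.58 against 0.45 h (median 4.5 h, CV 20%, n = 6).

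One late value can still separate the two. For {3, 4, 4, 8} h the median is 4.0 and the mean is 19/4 = 4.75. For {3, 4, 4, 4} h the median is again 4.0 and the mean is 15/4 = 3.75.

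**2. Do the listed statistics hide the spread?**

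Mean and SD alone can. {4,4,4,8,8,8} and {4,4,6,6,6,10} both have mean 36/6 = 6.00, SD √(24/5) = 2.19 and CV 36.5%, with ranges of 4 to 8 h and 4 to 10 h. But section 10.2.1 also lists the geometric mean, and this differs: 5.66 against 5.71.

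Listing every possible set of nominal times from 1 to 12 h gives 210 sets for n = 4, 462 for n = 5 and 924 for n = 6. Counting pairs that agree on mean and SD but differ in median or range, 18, 83 and 267 sets are involved. Requiring the exact geometric mean to agree as well leaves none at any of the three sample sizes. With recorded times tmax is not confined to these values, and printed figures are rounded, so this is no proof that the range can always be recovered from the summaries. It does show that this pair is no example of two sets with identical listed statistics.

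**3. Is anything lost?**

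Section 10.5.7 gives an individual tmax for each treated subject: at most six values per analyte. Sorting six numbers yields the median, minimum and maximum. Nothing in section 10.2.1 says that only the listed statistics may be reported.

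**The case for a change.** The strongest case for a change is that stating the summary in advance is better than leaving it to discretion, that the study's whole output is descriptive, and that the addition costs one sentence and no data. It is also true that a trial with one late peak could show a mean more than 0.5 h from its median, and that actual times are recorded without an explicit statement that tmax will be taken from them.

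Most of this is fair, but it shows no harm. Discretion matters where a choice could change a conclusion. Here the synopsis rules out formal comparisons, section 10.3.2 plans no tests, and section 10.1 names clearance and volume as the primary parameters. No section says that tmax will be set against the earlier medians. Such a reading would be informal in any case: the earlier studies used 10 mg and 18.8 mg under fasting conditions, whereas here the dose is 2.5 mg and "The study will be conducted with meals, snacks and beverages provided ad lib".

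On timing, three places require actual times and none calls for nominal times in the analysis, so the silence is no sign that the recorded times would be ignored.

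What stands is a preference for a more conventional tmax table.

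**Conclusion.** The reading of the text is correct: section 10.2.1 applies mean, geometric mean, SD and %CV to tmax and names no median or range, unlike the Introduction's account of earlier data. No change follows. This is missing detail that analysts will fill sensibly, with no gain to the study's conclusions from spelling it out. A sponsor who followed the plan to the letter would still report sound tmax results, and anyone wanting the median and range could take them from 4 to 6 individual values per analyte.

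The size is small: an average geometric-mean-to-median difference of -0.06 to +0.09 h, with individual trials differing by 0.5 h or more in about 2 to 28% of cases. These figures rest on an assumed lognormal tmax with CV 20 to 40% and on medians carried over from older children. The conclusion depends less on them than on three features of the plan: individual values are estimated, nothing excludes further statistics, and no test, formal comparison or decision rule uses tmax.

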10.2.2 Safety Endpoints

Safety endpoints will include the following:

All AEs; treatment-emergent AEs

10.3 General Considerations for Statistical Analysis

10.3.1 Analysis Populations

All treated subjects will be included in the analysis for safety and tolerability assessments. All subjects with sufficient plasma concentration data for estimating pharmacokinetic parameters will be included in the pharmacokinetic analyses.

10.3.2 Test Hypothesis and P Value Justification

No formal statistical tests are planned.

10.3.3 Procedures for Handling Missing Data

In general, no imputation will be done for missing data. However, AEs with missing severity assessments will be assigned as "severe," and AEs with missing relationship assessments will be assigned as "related" for the purpose of analysis.

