9.3 Collecting, Recording and Evaluating Adverse Events and Serious Adverse Events

The investigator will attempt to establish a diagnosis of the event on the basis of signs, symptoms, or other clinical information. In such cases, the diagnosis, not the individual signs or symptoms, should be documented as the AE or SAE. AEs will be collected from the point the Informed Consent is signed through EOT or Early Termination Visit.

Both total and treatment-emergent AEs will be reported. Treatment-emergent AEs are defined as those that occur after dosing of study medication until EOT or Early Termination Visit.

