9.3.2 Assessment of Causality

The investigator is obligated to use his or her clinical judgment to assess the relationship between the study medication and the occurrence of each AE or SAE. The investigator will assess the relationship to the study medication by using the following criteria:

- **Definitely Related**: An AE has a strong temporal relationship to the study drug. The AE is most likely explained by study drug. Dechallenge and rechallenge (if possible) are positive. The AE is consistent with a known response to the study drug. Another etiology is unlikely or significantly less likely
- **Probably Related**: An AE has a strong temporal relationship to the study drug. The AE is more likely explained by study drug than by another cause. Dechallenge (if performed) is positive
- **Possibly Related**: An AE has a reasonable temporal relationship to study drug. The AE could have been due to another equally likely cause; dechallenge is positive
- Not Related: The subject did not receive the study drug OR the AE has no temporal relationship to study drug OR the AE has a much more likely alternate etiology OR the AE is due to an underlying or concurrent illness or effect of another drug.

Even in situations in which minimal information is available for the initial SAE report, it is important that the investigator always makes an assessment of causality for every event before transmitting the SAE reporting form and AE CRF page(s) to the sponsor. The causality assessment is one of the criteria used when determining regulatory reporting requirements. The

investigator may change his or her opinion of causality in light of follow-up information and amend the SAE reporting form and AE CRF page(s) accordingly.

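### Section 10.3.3 assigns every AE with a missing relationship as related, with no limit to post-dose events, so a pre-dose AE could be analysed as drug-related (minor)

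*Combined protocol and SAP*

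**What the plan says.** All sections are in the combined protocol and SAP.

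- **Missing data (10.3.3).** The general rule is "In general, no imputation will be done for missing data". There are two exceptions, both for AEs. A missing severity becomes severe. For causality, "AEs with missing relationship assessments will be assigned as" related for the purpose of analysis. Neither exception mentions onset, dosing or treatment-emergent status.
- **AE collection (9.3).** "AEs will be collected from the point the Informed Consent is signed through EOT or Early Termination Visit". Section 5.1.1 and Table 2 in Appendix A schedule an AE assessment at Screening.
- **AE reporting (9.3 and 10.2.2).** "Both total and treatment-emergent AEs will be reported". The safety endpoints are given as "All AEs; treatment-emergent AEs".
- **Treatment-emergent definition (9.3).** "Treatment-emergent AEs are defined as those that occur after dosing of study medication until EOT or Early Termination Visit".
- **Safety population (10.3.1).** "All treated subjects will be included in the analysis for safety and tolerability assessments". The synopsis is wider and reports AEs for all subjects from enrolment.
- **Causality scale (9.3.2).** There are four levels: Definitely, Probably, Possibly and Not Related. Not Related includes the case "The subject did not receive the study drug OR the AE has no temporal relationship to study drug".

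**The concern.** Treating a missing causality assessment as related is a sensible worst-case convention once a subject has been exposed. Before exposure there is no worst case to guard against, because a single dose given later cannot have caused an event that preceded it. The rule in 10.3.3 makes no such distinction, and the plan deliberately collects and reports pre-dose events. A child who catches a cold during screening, and whose relationship field is left blank, would be carried into the analysis as having a drug-related AE.

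The stake is a false drug attribution in a very small paediatric dataset, where each child is a large fraction of the total. It would also be produced by following the plan as written, not by a departure from it.

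**Working it through.** The plan states no figure on this point, so the check is mainly a comparison of sections.

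**Step 1. Can a pre-dose AE be in the data?** Yes. Section 9.3 starts collection at consent, and Screening, with its AE assessment, can be up to 6 weeks before dosing.

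**Step 2. Does it enter a planned output?** Yes, the total-AE set (9.3, 10.2.2). It does not enter the treatment-emergent set, which is post-dose by definition.

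**Step 3. Does the analysis population remove it?** No. Section 10.3.1 selects subjects, not events, so a treated child's screening events stay in.

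**Step 4. What does 10.3.3 assign if the relationship is blank?** Related, whatever the onset.

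**Step 5. What would 9.3.2 give for the same event?** Not Related. For a child dosed later, the limb on absence of a temporal relationship applies. For a child enrolled but never dosed, whom the synopsis wording could include, the limb on not having received the drug applies.

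**Step 6. Does any other section block the assignment?** No. Section 10.5.2 covers only MedDRA coding by system organ class and preferred term. Section 9.2.1 covers pre-dose SAEs, where the question is relation to study participation, but it concerns which SAEs are reported to the sponsor. It does not say how a blank relationship is analysed.

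For a pre-dose AE with a blank relationship, the two sections therefore give opposite answers, and only 9.3.2 is tenable.

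**Size if a relationship display of total AEs is produced.** The input is the planned sample of 4 to 6 subjects. With no other related AE, one misassigned child moves the proportion with a related AE from 0 to 1/n:

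- n = 6: 1/6 = 16.7%
- n = 4: 1/4 = 25.0%

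**The case against.** The strongest reply is that the gap may never affect a result.

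- **No relationship table is specified.** Section 10.5.2 plans classification by system organ class and preferred term, and neither safety endpoint is split by relationship. Assigning related to a blank changes neither the count of all AEs nor the count of treatment-emergent AEs. This stands, and it confines the effect to a relationship display or listing that the plan does not describe. It is not a complete answer: 10.3.3 makes the assignment for the purpose of analysis, so some use of relationship is foreseen.
- **Blanks should be rare.** Section 9.3.2 obliges the investigator to assess each AE and offers a fitting answer for a pre-dose event. Section 11.3 makes the investigator responsible for complete eCRF sections and plans 100% source verification. With 4 to 6 children, a blank is easily queried. This also stands. But a missing-data rule matters only when those safeguards have failed, and in that case this one gives the wrong value.
- **The rule errs on the cautious side, and dates would expose the error.** This is true of a reader who looks at individual listings. It is a reason for low priority, not for keeping the rule.

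A reader might also infer from the length of screening that nearly all affected AEs would be pre-dose. Six weeks is 42 × 24 = 1008 h, against about 28 h after dosing, and 1008/(1008 + 28) = 97.3%. The documents do not support that inference. The figure is a share of calendar time at the maximum screening length; with one week of screening it is 168/196 = 85.7%. It becomes a share of AEs only with a constant event rate and equal ascertainment, yet Table 2 has one AE assessment at Screening against ten at Day 1 and Day 2 time points. Above all, it says nothing about how many relationship fields will be blank, and those are the only events the rule touches.

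**Conclusion.** The rule in 10.3.3 is wrong as written for pre-dose AEs. It would give an event with a blank relationship a value that 9.3.2 rules out, and nothing else in the plan prevents this.

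The consequence is small. It requires a pre-dose AE whose relationship is missing and remains missing after query and source verification, and it shows only in a relationship display or listing of total AEs. On the assumptions that such a display is produced and that one child is misassigned, that child is 17% to 25% of the sample.

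A reader might go further and conclude that the drug-related AE rate of this trial is at risk, or that the safety conclusions are. The documents do not support that: no such rate is specified, treatment-emergent summaries exclude pre-dose events, no formal tests are planned (10.3.2), and the PK endpoints do not use the rule. The priority is minor.

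**What to change.** Replace the relationship part of the rule in 10.3.3 with: *Treatment-emergent AEs with missing relationship will be assigned as related; AEs with onset before dosing will be classed as Not Related to study medication, consistent with 9.3.2.*

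As a matter of completeness only, the same edit could state which of the four levels in 9.3.2 make up related, since the scale has no level of that name.

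The cost is one sentence in the statistical section, with no new data, no added work for sites and no change to how children are managed. Worst-case handling of post-dose events is kept in full.
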